#### 9.4 Evaluability for Response

Eligible patients assigned to Arm LMP-TC will be considered evaluable for the primary endpoint (percentage successfully matched and treated). All 3 Cohorts will be combined into a single set of patients for the analysis.

All eligible patients will be evaluable for Aims 1.2.1, 1.2.8, and 1.3.2. For Aim 1.2.1, all patients who submit HLA typing by the end of the trial will be evaluable, regardless of the timing of the submission.

Any eligible patient who receives at least one dose of RTX will be considered evaluable for Aims 1.2.2–1.2.4 and 1.2.6.

Any eligible patient who receives at least one dose of LMP-specific T cells will be considered evaluable for Aims 1.2.5, 1.2.7, 1.3.1, and 1.3.3.

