## ABSTRACT

This is a pilot study of Rituximab (RTX) with or without Third Party Latent Membrane Protein (LMP)-specific Cytotoxic T-Lymphocytes (LMP-specific T cells or LMP-TC) in pediatric and young adult solid organ transplant recipients (SOT) with newly diagnosed, relapsed or refractory EBV-Positive CD20-Positive Post-Transplant Lymphoproliferative Disease (PTLD). EBV-positive PTLD has become the most common form of lymphoproliferation in childhood with an estimated annual incidence of > 100 newly diagnosed patients < 18 years of age in the US. Reduction of immunosuppression with the goal to restore the immunological function of cytotoxic T cells is the first-line therapy with response rates between 20-80% but carries the risk of rejection. Patients who do not respond to reduction of immunosuppression require further therapy and addressing the underlying immunological defect is the next logical step. Preliminary studies have shown that EBV-specific T cells can repair the underlying immunological defect, are well tolerated and have efficacy in PTLD. This pilot study is testing the hypothesis that it is feasible to use Third Party LMP-specific T cells in a cooperative group setting. The production of LMP-specific T cells has become a reproducible procedure with standardized SOPs to generate Good Manufacturing Practice (GMP)-grade LMP-specific T cells. Third Party LMP-specific T cells are readily produced from healthy donors, HLA typed and cryopreserved in cell banks. A Third Party LMP-specific T cells bank, mostly derived from healthy donors, has been established at the Program for Cell Enhancement and Technologies for Immunotherapy (CETI) at Children's National Medical Center and will supply LMP-specific T cells for this study. Untreated newly diagnosed (Cohort A) and relapsed (Cohort B) patients will receive three weekly doses of rituximab followed by a response assessment. Newly diagnosed patients who have a complete response (CR) to rituximab will receive an additional three doses of rituximab because they are predicted to have an excellent outcome. Newly diagnosed patients who do not achieve a CR to 3 doses of rituximab and all relapsed PTLD patients regardless of response will receive LMP-specific T cells. Patients with refractory and/or persistent disease after rituximab according to institutional guidelines are eligible for Cohort C and will proceed straight to LMP-T cell therapy. The closest HLA matched LMP-specific T-cell product will be identified for each patient. At least a 1/6 HLA match with activity through the shared alleles is required. Based on previous experience, it is expected that about 30 different HLA characterized products will cover > 90% of the eligible patients. Participating institutions in this limited institution study will have FACT accredited cell processing and storage facilities and have to adhere to SOPs about dispensing and infusing LMP-specific T cells.

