### 1.2 Secondary Aims

- 1.2.1 To determine the percentage of eligible patients for whom a suitable LMP-specific T-cell product derived from a Third Party LMP-specific T-cell bank is available.
- 1.2.2 To estimate the response rate (RR) to three doses of RTX as single agent in children and young adults with newly diagnosed or relapsed EBV-Positive CD20-Positive PTLD after solid organ transplantation (SOT).
- 1.2.3 To estimate the 2-year event-free survival (EFS) of children and young adults with newly diagnosed, refractory or relapsed EBV-Positive CD20-Positive PTLD after SOT treated with RTX and/or LMP-specific T cells.
- 1.2.4 To estimate overall survival (OS) of children and young adults with newly diagnosed, refractory or relapsed EBV-Positive CD20-Positive PTLD after SOT treated with RTX and/or LMP-specific T cells.
- 1.2.5 To estimate the RR to LMP-specific T cells of newly diagnosed (without complete response to Course RTX1), refractory, and relapsed children and young adults with EBV-Positive CD20-Positive PTLD.
- 1.2.6 To estimate progression-free survival (PFS) of children and young adults with newly diagnosed, refractory or relapsed EBV-Positive CD20-Positive PTLD after SOT treated with RTX and/or LMP-specific T cells.
- 1.2.7 To describe the toxicity of Third Party LMP-specific T cells in children and young adults with newly diagnosed, refractory or relapsed EBV-Positive CD20-Positive PTLD after SOT treated with RTX and/or LMP-specific T cells.
- 1.2.8 To validate that absence of EBV viremia correlates with RR, EFS and OS.

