##### 4.1.2.2 **Arm LMP-TC**

**Cohort A:** Newly diagnosed patients who do not achieve a complete response (CR) after Induction will be assigned to Arm LMP-TC.

**Cohort B:** All relapsed patients will be assigned to Arm LMP-TC after induction regardless of response.

**Cohort C:** All patients with refractory disease who have received rituximab (or biosimilar) within 90 days according to institutional guidelines are assigned to Cohort C and proceed directly to Arm LMP-

TC at enrollment.

Patients assigned to Arm LMP-TC without a suitable LMP-specific T-cell product will go off protocol therapy. Further treatment with chemotherapy is at the discretion of the treating physician.

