## 9.3 Methods of Analysis

For the primary endpoint, the point estimate of the proportion successfully matched and treated (among all 3 Cohorts combined) will be the uniformly minimum variance unbiased estimator, and an exact one-sided binomial 95% confidence interval (adjusted for the interim analysis by the method of Jung and Kim)[37](#) will be used to get a lower bound for the actual rate of successful treatments as defined in the primary objective.

For the secondary endpoints:

- The proportion of eligible patients who are successfully matched will be assessed using the uniformly minimum variance unbiased estimator for the proportion and an exact one-sided binomial 95% confidence interval (adjusted for the interim analysis by the method of Jung and Kim) to get a lower bound for the actual rate.
- PFS (defined as time to first occurrence of progression or death (events) or loss to follow-up or survival to analysis date (non-events)), EFS (defined as time to first occurrence of relapse, second/secondary malignant neoplasm (SMN), death (events) or loss to follow-up or survival to analysis date (non-events)), and OS (defined as time to death (event) or loss to follow-up or survival to analysis date (non-events)) will be assessed using Kaplan-Meier estimates, both for all patients combined and also separately in each Cohort. Aim 1.2.8 will be assessed using the Log-Rank test for EFS and OS and the exact conditional test of proportions (Fisher's Exact test) for RR, both for all patients combined and stratified by Cohort.
- Response rates will be assessed using exact two-sided binomial 95% confidence intervals to get estimates of the response rate. Aim 1.2.2 will be evaluated in Cohorts A and B only (combined and separately), with response classified by comparing disease evaluation at the Week 3 evaluation to the baseline of disease evaluation at study entry using the criteria in Section 10.2. Patients with CR will be considered responders. For Aim 1.2.5, response will be classified by comparing disease evaluation at the Week 6 of LMP-CT1 evaluation to the baseline of disease evaluation at the Week 3 evaluation using the criteria in Section 10.2, both in all Cohorts combined and in each Cohort separately. Patients with CR or PR will be considered responders.
- Toxicities will be described using descriptive statistics. Toxicity monitoring and analysis will be performed based on "as treated".

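### Section 9.4 makes evaluability for EFS, OS and PFS depend on a dose of rituximab, which on its natural reading drops Cohort C from three aims that name refractory patients

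*Combined protocol and SAP*

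**What the plan says.** Section 9.4 assigns an evaluable population to each aim. For the rituximab response rate (1.2.2), EFS (1.2.3), OS (1.2.4) and PFS (1.2.6) the rule is: "Any eligible patient who receives at least one dose of RTX will be considered evaluable for Aims 1.2.2–1.2.4 and 1.2.6". It does not say whether the dose has to be given on study. A separate rule in 9.4, for recipients of LMP-specific T cells, covers Aims 1.2.5, 1.2.7, 1.3.1 and 1.3.3. Another reads: "All eligible patients will be evaluable for Aims 1.2.1, 1.2.8, and 1.3.2".

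Aim 1.2.3 is "To estimate the 2-year event-free survival (EFS) of children and young adults with newly diagnosed, refractory or relapsed EBV-Positive CD20-Positive PTLD". Aims 1.2.4 and 1.2.6 name the same three disease groups, and all three aims describe treatment as rituximab, T cells or both.

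Section 9.3 says that PFS, EFS and OS "will be assessed using Kaplan-Meier estimates, both for all patients combined and also separately in each Cohort". It limits the rituximab response rate separately: "Aim 1.2.2 will be evaluated in Cohorts A and B only (combined and separately").

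On treatment, the Abstract says that patients with refractory or persistent disease after rituximab "are eligible for Cohort C and will proceed straight to LMP-T cell therapy". Section 4.1.2.2 says that they "are assigned to Cohort C and proceed directly to Arm" LMP-TC at enrolment.

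**The concern.** The evaluability rule for the three time-to-event aims turns on a drug that one of the three cohorts does not receive on protocol. Followed as written, with the dose taken to be on study, the rule leaves the Cohort C curves for EFS, OS and PFS without patients. Estimates labelled as combined would describe Cohorts A and B alone. Cohort C is also the only cohort treated on protocol with T cells and no rituximab, so its outcomes cannot be read from the other two.

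The sections also disagree about who counts for EFS and OS. Under Aim 1.2.8, "Aim 1.2.8 will be assessed using the Log-Rank test for EFS and OS" in all eligible patients. On the on-study reading Cohort C would therefore be in the EFS and OS tests but outside the EFS and OS estimates. An analyst would have to follow 9.4 and lose a cohort, or depart from it with no written rule for doing so.

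**Working it through.** No stated figure is in dispute. The check sets the sections side by side and then counts the planned estimates affected.

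**1. Does Cohort C receive rituximab on protocol?** No.
- The first course (RTX1) is for Cohorts A and B (4.2); 10.2.1 describes it as for non-refractory patients.
- The second course (RTX2) is for newly diagnosed patients in complete response (4.1.2.1, 4.3.1).
- Cohort C starts with T cells (Abstract, 4.1.2.2).
- Cohort C rituximab was given before enrolment: 3.2.5 requires at least 3 weekly doses in the preceding 90 days.

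**2. Does another rule in 9.4 bring Cohort C back?** No. The rule for T-cell recipients does not list Aims 1.2.3, 1.2.4 or 1.2.6.

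**3. Reading 1: the dose must be on study.** Two points favour this reading. The parallel rule for LMP-specific T cells uses the same construction and can only mean on-study dosing. The rituximab rule also governs Aim 1.2.2, which concerns response to on-study rituximab. The evaluable Cohort C set is then 0.

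**4. Count of planned estimates under Reading 1.**
- Endpoints in 9.3: PFS, EFS, OS = 3.
- Sets per endpoint: combined, A, B, C = 4.
- Planned estimates: 3 × 4 = 12.

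| Set | Estimates | Effect |
|---|---|---|
| Cohort C | 3 | no patients |
| Combined | 3 | Cohorts A and B only |
| Cohort A alone | 3 | unchanged |
| Cohort B alone | 3 | unchanged |

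Affected: 3 + 3 = 6 of 12.

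**5. Reading 2: pre-enrolment rituximab counts.** This is arguable, because the separate limit on Aim 1.2.2 in 9.3 would be unnecessary if 9.4 already left Cohort C out. But 3.2.5 means that every eligible Cohort C patient meets the condition, so it screens out nobody in that cohort. It also admits any Cohort C patient never treated on study, for example for want of a suitable product (4.1.2.2). Such a patient goes off study under 8.2(f). PFS under 10.2.9 runs from the start of treatment, so that patient has no PFS start date.

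The Abstract expects the product bank to cover more than 90% of eligible patients. If that holds in Cohort C, lack of a product alone would leave less than 100% − 90% = 10% of the cohort untreated. Other routes to no treatment, such as refusal, would add to this. Under Reading 2 the same 6 estimates could include these patients.

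**6. What is not affected.** Primary evaluability rests on assignment to Arm LMP-TC. Aims 1.2.1, 1.2.5 and 1.2.7 and the monitoring rules do not use the rituximab condition.

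**The case against.** The strongest reply is that the intent is plain. The aims name refractory patients, and 9.3 asks for a curve in each Cohort, so an analyst is unlikely to deliver an empty one. Section 9.4 also never states that Cohort C is excluded; it says who is included. On this view the point is a minor clarification.

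The intent is indeed clear, and 9.4 contains no explicit exclusion. But a list of who is evaluable for each aim is normally read as complete. Clear intent elsewhere shows that 9.4 is the passage at fault; it does not supply a rule to use in its place.

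Three narrower objections have some force:
- The separate limit on Aim 1.2.2 can be argued either way. It is redundant if 9.4 already excludes Cohort C, and necessary if 9.4 includes it. It does not settle which reading was meant.
- Under Reading 2, never-treated patients leave the study, so they would be censored almost at once and would barely move a Kaplan-Meier estimate. What remains is the undefined PFS start and a condition that does nothing in Cohort C.
- The count of 6 of 12 describes planned estimates. It measures neither patients nor bias.

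**Conclusion.** The concern holds and should be fixed. On the on-study reading, 9.4 contradicts Aims 1.2.3, 1.2.4 and 1.2.6 and the analysis in 9.3: three planned estimates have no patients and three others lose a cohort. On the alternative reading, the condition has no effect in Cohort C and lets in patients with no PFS start date. Neither reading gives a workable population.

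The inconsistency itself is established with high confidence; which reading the authors meant is less certain. The documents do not give the Cohort C share of enrolment, so the number of patients involved and the size and direction of any bias cannot be derived. The figure of under 10% rests on carrying the plan's overall product-coverage expectation over to Cohort C. The consequence is confined to secondary descriptive estimates.

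**What to change.** Split the sentence in 9.4 into two rules:

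1. Aim 1.2.2: eligible Cohort A and B patients given one or more doses of rituximab on protocol.
2. Aims 1.2.3, 1.2.4 and 1.2.6: eligible patients in any Cohort given one or more doses of protocol therapy, whether rituximab or LMP-specific T cells.

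Sections 9.5 and 10.2.4.2 already use the protocol-therapy condition. It removes the difficulty under both readings and leaves the Cohort A and Cohort B estimates as they are. Report, by Cohort, how many eligible patients are left out because they were never treated.

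The Aim 1.2.8 population can stay as it is. A small difference then remains, because never-treated eligible patients would be in its tests but outside the EFS and OS estimates; the reported counts would show how many. If that population is changed, change it for response rate, EFS and OS together.

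The cost is one sentence becoming two. No new data are needed, since treated Cohort C patients are already followed until they meet an off-study criterion (8.1, 8.2).

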For cytokine release syndrome and graft versus host disease, the analytic unit for monitoring for protocol-specific toxicities will be the patient-course. Each course where the patient receives the agent or where a protocol-specific toxicity event is observed will be considered in the analysis. We will assume a beta prior distribution with  $\alpha = 0.6$  and  $\beta = 1.4$  and an unacceptable toxicity rate of  $p_0 = 30\%$ . At least once per month, we will calculate the posterior probability (given the data) that the probability of protocol-specific toxicity exceeds the 30% threshold, *i.e.*,  $P(p > 0.3 | \text{Data})$ . If there is a posterior probability of 80% that the toxicity rate is at least 30%, then accrual will be suspended pending review by DSMC. Examples of situations in which this rule will indicate protocol-specific toxicities have been noted and are presented below:

Number of failures	Number of patient-cycles
2	3
3	6
4	8
5	11
6	14
7	17
8	20
9	23
10	26
11	29
12	32
13	35
14	38

Interim monitoring will also be performed to watch for a 20% progression rate at week 10 in newly-diagnosed patients and a 40% progression rate at week 10 for relapsed and refractory patients. For newly-diagnosed patients, the beta parameters will be  $\alpha = 0.52$  and  $\beta = 2.08$ ; and for relapsed and refractory patients the beta parameters will be  $\alpha = 1.04$  and  $\beta = 1.56$ ; if there is a posterior probability of 80% that the progression rate at week 10 is at least 20% for newly-diagnosed patients or 40% for relapsed/refractory patients, then accrual for the respective cohort or cohorts will be suspended pending review by the DSMC. The stopping rule will be triggered as described in the following table:

Number of failures	Number of newly-diagnosed patients	Number of relapsed/refractory patients
2	4	2
3	8	4
4	12	6
5	16	8

6	20	11
7	24	13
8	29	15
9	33	17
10	38	19

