#### 9.5 Evaluability for Toxicity

A patient will be considered for toxicity monitoring if the patient is eligible, receives at least one dose of protocol therapy, and one of the following occurs: (1) completes a full cycle of therapy with no toxicities; (2) dies on protocol therapy for a reason considered possibly, probably, or likely related to protocol therapy; or (3) experiences an adverse experience possibly, probably, or likely related to one of the agents. A toxicity-evaluable patient will be considered in the analysis during the interval from study enrollment until protocol therapy is terminated or a toxicity-event is observed, whichever occurs first. A toxicity-evaluable patient will be considered to have experienced a protocol-specific toxicity event if: (1) the patient dies on protocol therapy for a reason considered possibly, probably, or likely related to protocol therapy; or (2) experiences a dose-limiting toxicity.

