#### 10.2.4 Definitions

10.2.4.1 Evaluable for toxicity: A patient will be considered for toxicity monitoring if the patient is eligible and one of the following occurs: (1) completes one course of protocol therapy; (2) dies on protocol therapy for a reason considered possibly, probably, or likely related to protocol therapy; or (3) is removed from protocol therapy because of an adverse

experience possibly, probably, or likely related to one of the agents.

10.2.4.2 **Evaluable for objective response:** Only those patients who have measurable disease present at baseline and have received at least one dose of protocol therapy will be considered evaluable for response. These patients will have their response classified according to the definitions stated below. (Note: Patients who exhibit objective disease progression prior to the end of Course 1 will also be considered evaluable.)

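### Section 9.4 limits the T-cell toxicity aim (1.2.7) to eligible patients, so an infused patient later ruled ineligible is left out of the harm summary

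*Combined protocol and SAP*

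**What the plan says.** Aim 1.2.7 (Section 1.2) is to describe the toxicity of the third-party T cells. Section 9.4 sets its population: "Any eligible patient who receives at least one dose of LMP-specific T cells will be considered evaluable for Aims 1.2.5, 1.2.7". The same sentence covers the response aim, 1.2.5.

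Section 9.3 says "Toxicity monitoring and analysis will be performed based on" an as-treated principle. It does not define that term and does not mention eligibility.

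Three places bear on the monthly CRS/GvHD suspension rule:

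- Section 9.3 makes the patient-course the unit and says: "Each course where the patient receives the agent or where a protocol-specific toxicity event is observed will be considered in the analysis". It sets no eligibility condition.
- Section 9.5 says: "A patient will be considered for toxicity monitoring if the patient is eligible, receives at least one dose of protocol therapy", and one of three things must also hold. Either the patient "completes a full cycle of therapy with no toxicities", or there is a related death, or there is a related adverse experience. Follow-up for this purpose runs "until protocol therapy is terminated or a toxicity-event is observed, whichever occurs first".
- Section 10.2.4.1 says: "A patient will be considered for toxicity monitoring if the patient is eligible and one of the following occurs". Its first condition is that the patient "completes one course of protocol therapy". Its third requires removal from therapy for a related adverse experience.

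Section 3.2 says the criteria are read literally, cannot be waived, and are checked against source records at audit. Section 3.1.5 makes anyone who began protocol therapy before enrollment ineligible.

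**The concern.** An eligibility condition is reasonable for response, where the question concerns the target population. It fits poorly with a description of harm: a reaction to the product is information about the product, whether or not an entry criterion later proves unmet. A statistician who follows Section 9.4 to the letter would drop such a patient from the Aim 1.2.7 table. With about 30 infused patients, one omission can remove the only event of its kind.

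A lesser point concerns the suspension rule. Section 9.3 counts courses without regard to eligibility, while 9.5 and 10.2.4.1 each require it, and no sentence links the three. Two statisticians could feed slightly different courses into the same posterior.

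**Working it through.** **1. The texts side by side.** Take a patient who received T cells and is later ruled ineligible.

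| Place | Is the patient counted? |
|---|---|
| 9.4, Aim 1.2.7 | No |
| 9.3, as-treated statement | Unclear; the term could mean only grouping by treatment received |
| 9.3, CRS/GvHD course count | Yes |
| 9.5 and 10.2.4.1 | No |

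**2. How often it could arise.** The documents give neither an ineligibility rate q nor an event rate e, so both are assumed. I take 30 infused patients, from the target of at least 30 assigned to Arm LMP-TC in Section 9.2. The number infused could differ.

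- P(no infused patient ineligible) = (1 − q)^30 = 55%, 21% and 4% at q = 2%, 5% and 10%.
- Expected number of patients with an event who are left out = 30 × q × e. At q = 5% and e = 10% this is 30 × 0.05 × 0.10 = 0.15, and P(at least one) = 1 − (1 − 0.005)^30 = 14%.
- Range: 30 × 0.02 × 0.05 = 0.03 to 30 × 0.10 × 0.30 = 0.9.

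**3. Effect on the harm table** (two-sided Clopper-Pearson 95% intervals, for illustration; Section 9.3 plans only descriptive statistics for toxicity).

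| All infused | One patient excluded |
|---|---|
| 1/30 = 3.3% (0.1% to 17.2%) | the event excluded: 0/29 = 0% (0% to 11.9%) |
| 3/30 = 10.0% (2.1% to 26.5%) | one event excluded: 2/29 = 6.9% (0.8% to 22.8%) |
| 3/30 = 10.0% (2.1% to 26.5%) | a non-event patient excluded: 3/29 = 10.3% (2.2% to 27.4%) |

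**4. Effect on the CRS/GvHD rule.** Inputs from Section 9.3: prior Beta(0.6, 1.4), threshold 30%, suspension at posterior probability 80%. With x events in n courses, the posterior probability is 1 − F(0.3), where F is the distribution function of Beta(0.6 + x, 1.4 + n − x).

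The plan's own table reproduces. For each x, the largest n with posterior at or above 0.80 matches all 13 rows: 2/3 gives 0.838, 3/6 gives 0.800 and 14/38 gives 0.801. The formula is sound; the only question is which courses enter it.

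Now drop each course with probability 10%, independently of outcome, and check the rule after every course, for 30 courses in 100,000 simulated trials:

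| True event rate | Suspension probability, all courses | Eligible only |
|---|---|---|
| 20% | 18.9% | 18.7% |
| 30% | 49.9% | 48.8% |
| 40% | 82.2% | 80.2% |

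The largest shift is 82.2 − 80.2 = 2.0 points. An exact recursion for the all-courses column gives 18.9%, 50.1% and 82.3%, which agrees within simulation error. With 5% ineligible and a true rate of 10%, suspension is 3.7% under either count.

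In a single trial sitting on a boundary, removing one event course takes every one of the 13 rows below 0.80 (to between 0.626 and 0.731). That is nearly automatic at a minimal boundary and does not show a likely impact.

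**The case against.** The case for leaving the text alone has several parts.

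- **The as-treated statement leaves room to report all infused patients.** It does, but it is undefined, while 9.4 says eligible outright. The specific wording would normally prevail.
- **Section 9.3 already settles the CRS/GvHD rule.** It is the text written for that rule and gives the unit, the courses counted, the prior and the trigger. Sections 9.5 and 10.2.4.1 are general definitions, and the latter sits under response criteria. This largely stands, so the second point is one of clarity and not a contradiction.
- **Patients are protected anyway.** This stands. Routine adverse event reporting (11.12) and expedited reporting (11.10) carry no eligibility condition. Enrollment is suspended for review if any patient has suspected allograft failure or rejection (9.3), and the data and safety monitoring committee reviews toxicity (12.2). None of these, however, defines the denominator of the Aim 1.2.7 summary.

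Two stronger readings are tempting, and the documents do not support either.

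- A reader might infer that retrospective central pathology review will turn infused patients ineligible. Section 13.1 says its results do not go back to sites, 14.1 makes submission of material optional, and nothing says the review alters eligibility.
- A reader might infer that the completion conditions in 9.5 and 10.2.4.1 strip event-free T-cell courses from the rule and so inflate suspensions. Those conditions apply to patients, not courses. Cohorts A and B receive a full rituximab course before any T cells (4.1.1, 4.1.2), and patients who do not tolerate all doses leave protocol therapy (5.2). Most of those who reach the T cells have therefore already met the conditions. Modelling them as a course-level filter would overstate the effect.

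**Conclusion.** The point holds as a minor correction to the harm population. Section 9.4, as written, omits an infused patient later found ineligible from the Aim 1.2.7 summary, and 9.3 does not clearly restore that patient. The affected group may be empty. If it is not, one exclusion can turn a single observed event into none (1/30 to 0/29) in a study of this size.

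For the CRS/GvHD rule the eligibility condition hardly matters: at most about 2 points in suspension probability, assuming 10% ineligible at random and true event rates of 20% to 40%. A trigger in any case only suspends accrual pending committee review. All these sizes rest on assumed rates and on 30 infused patients or 30 courses. The documents do not support a claim that safety oversight of individual patients is weakened.

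**What to change.** In Section 9.4, take Aim 1.2.7 out of the sentence on eligible patients and add: *All patients given one or more infusions of LMP-specific T cells are evaluable for Aim 1.2.7, whether or not they are later found ineligible.* State in the toxicity table how many infused patients were ineligible.

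In Sections 9.5 and 10.2.4.1, add a cross-reference: *For the CRS/GvHD rule, courses are counted as set out in Section 9.3, regardless of eligibility.* Keep the eligibility condition for the primary, response and survival aims.

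The cost is wording only. Ineligibility is not an off-study criterion in 8.2, and 11.12 collects adverse events without regard to it, so no new data are needed. The one drawback is that the toxicity table may include a few patients outside the target population; the reported count makes that visible.
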